It is also possible that some patients will feel tired and will not be able to go through all the tests inside the MRI scanner. In this case, we will stop as based on participants' level of fatigue. We will try to have similar number of tests across 4 clinical visits.

I would like to mention here that given the complexity of this study, we expect that some of the tasks/procedures will be omitted or not completed during each of the 5 visits. We do not expect that all patients perform all the tasks described above (inside or outside the MRI scanner). We will try our best to test participants on all these tasks above but we could face some challenges and decide not to complete them. For instance, we will be based on the fatigue level of patients and patients' feedback to make these decisions. The level of fatigue varies from one participant to another.

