### **Randomization and blinding**

**Clinical trial for ASD subjects:** The trial will be a double-blind, placebo-controlled, several doses of oxytocin, within subject design study. Patients will undergo 4 clinical visits (in addition to a first pre-clinical visit) during which they receive 12 puffs (6 in each nostril) of 8IU total, 24IU and 48IU oxytocin (syntocinon) and placebo (assigned randomly). The placebo will contain the same ingredients as syntocinon, except the active molecule oxytocin. This is essential for making sure that the patient does not recognize the type of treatment he is receiving. Hence, both patients and the experimenter will be blind to the type of the treatment administered.

The pharmacy IDS of Emory will be in charge of the randomization sequence and one of the staff members of the team (who is not involved in testing procedures) will be de-blinded.

We will break the blind after testing 25 patients with ASD to check the results half-way for a mid-point analysis. The mid-point analysis will focus on measures where effect sizes are anticipated to be large enough that the risk of false positives is minimal. We are expecting larger effect size on some measures and therefore we break the blind for those measures to be analyzed and published. Additional data on these measures will continue to be collected and we will attempt to publish the combined analysis at the end to avoid publication bias.

However, the data collection will continue until a sample size equal to 50. Given that we are facing challenges with ASD recruitment and that the study requires the participation in 5 long visits, it is possible that the study will stop at N=30 or 40, in case the PI was not able to recruit more ASD. We also expect dropouts after recruitment. We believe that we will be able to test 30 patients with ASD.

It is possible that this project will be funded by other grant funds which will allow adding more participants (more 50 ASD). In this case, the PI will submit an amendment accordingly.

**Healthy subjects:** There will be only one clinical visit for healthy subjects and they will all receive placebo spray (12 puffs, 6 per nostril). The study will be conducted in a single-blind design. The PI is aware that the subject is receiving placebo. However, the participant will be told that he might

receive oxytocin or placebo. This is important in order to control for the placebo effect on behavior and brain activity.

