Given that this project is the continuity of the previous IRB protocol 64623, we will contact healthy subjects and patients with autism that were already recruited in this previous protocol. We are planning to contact those who gave us approval to be contacted (in the consent form). We will go through the screening process (see above for more details) over the phone with the patient and family member if necessary and make sure he is interested and he is eligible for the study. The study coordinator will then schedule them for the first pre-clinical visit.

If a subject withdraws from the study, we will prepare a note to file (and put it in the regulatory binder) and report to the IRB during the continuing review.

We expect to recruit at least 30 patients with autism and 20 healthy controls. We expect a drop off of patients with ASD given that they need to come for 5 visits.

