*The secondary outcome measure* consists of correlating the effects of treatments on rsFC with the clinical improvements following treatments and post scan in ASD. The variables consist of BB-CGI clinical score (that will be rated blindly by a physician) and a socio-emotional behavioral score (rated by PI or staff blindly) during the BB-CGI. These two variables will be analyzed separately as they are dependent (based on the same test) but answer two different questions. We will conduct correlation analysis (Spearman or Pearson) between TEE-OXT or OXT-effect on rsFC and behavioral and clinical improvements. Behavioral variables will include: emotional responses, gestures, eye contact with experimenter and synchrony).

**For aim 2:** *The primary outcome measure of the second aim* consists of investigating the differences between the effects of the different treatments on BOLD activity of socio-emotional brain regions in response to social cues (Face perception task) in ASD. ROI analysis will include regions such as inferior occipital cortex, fusiform gyrus, superior temporal cortex, intra-parietal sulcus, superior parietal lobule, nucleus accumbens, amygdala and OFC). In this analysis, we have two variables that we will contrast (BOLD signal in response to emotional faces versus

neutral faces) and 4 treatment conditions within subject design (8IU, 24IU, 48IU and placebo) with covariates (order of visits to control for familiarity effects given that the treatment conditions are completely randomized). The presence of TEE-OXT will consist of finding differences between different treatment conditions of OXT and not only between OXT and placebo. We will also compare each of these OXT treatments with placebo condition separately to study OXT-effect.

*The secondary outcome measure* will consist of studying the effects of different treatments on a behavioral measure that is recorded during the MRI scan of the FPT: visual fixation duration on facial stimuli. Here, we have one variable (duration of visual fixation or eye gaze on emotional and neutral faces) and 4 treatment conditions. We will analyze the data with ANOVA repeated measures for determining TEE-OXT and t-tests for simple OXT-effects.

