Withdrawals, missing data and ineligible patients will be stated. Data will be controlled and double checked by the PI before publishing papers. Outliers will be investigated with statistical tools. Post-analysis will be checked for quality and checked for confounder factors, covariates. Additional precision on the type of analysis (behavioral, physiological and brain) will be submitted as amendments once the PI and staff members start working on the analysis of the data of the project.

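### Four-condition ANOVAs carry no rule for missing sessions, and gaze and social learning carry no visit term; a mixed model on all sessions would recover some precision at little cost (minor).

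*Combined protocol and SAP*

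**What the plan says.** All places are in the combined protocol and SAP.

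**Planned tests (Statistical analysis).**
- Gaze during the face task (aim 2, secondary): "We will analyze the data with ANOVA repeated measures for determining TEE-OXT and t-tests for simple OXT-effects". TEE-OXT is the plan's term for any difference between oxytocin doses.
- Repeated-measures ANOVA is also named for between-network resting connectivity (aim 1), ball-game BOLD (aim 3) and plasma oxytocin (aim 5 in this section, Aim 4 under Objectives).
- Social learning (aim 3, secondary) is to be analysed by ANOVA and t-tests.

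**Visit terms.** Visit order is a covariate in the aim 1 connectivity models, in the aim 2 BOLD model (reason given: familiarity) and in the aim 3 BOLD model (reason given: habituation). None is stated for gaze, social learning or plasma.

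**Expected incompleteness.**
- Clinical visits for ASD, after Table 2: "We do not expect that all patients perform all the tasks described above (inside or outside the MRI scanner". The preceding paragraph adds "We will try to have similar number of tests across 4 clinical visits".
- Participant selection: "We expect a drop off of patients with ASD given that they need to come for 5 visits".
- Randomization and blinding: "We believe that we will be able to test 30 patients with ASD".

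**Missing-data text (end of Statistical analysis).** "Withdrawals, missing data and ineligible patients will be stated". The same paragraph promises a general check of confounders and covariates, and says "Additional precision on the type of analysis (behavioral, physiological and brain) will be submitted as amendments".

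**The concern.** Differences between doses are the central question, and for gaze that question is assigned to repeated-measures ANOVA. In its classical form that test uses only patients observed under all four conditions. In a small crossover whose authors expect skipped tasks and dropout, it can discard usable sessions. The plan does not say how a patient with two or three sessions enters a four-condition test, so that choice could be made after results are known.

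Gaze is recorded during the same face task whose BOLD model is adjusted for familiarity, yet gaze itself has no stated adjustment. If gaze or reaction time drifts over four visits, the drift stays in the error term.

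**Working it through.** The plan gives no missing-session rate, drift or correlation between sessions, so it has no figure of its own to reproduce here.

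**Inputs from the documents:** four conditions per patient, randomized order, about 30 patients with autism.

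**Assumed:** correlation ρ = 0.5 between sessions, equal variances and correlations, 5/10/15/20% of sessions missing, no drift unless stated.

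**1. Patients with all four sessions.** If sessions are missing independently with probability q, the expected number is 30(1−q)⁴:
- q = 5%: 30 × 0.8145 = 24.4
- q = 10%: 30 × 0.6561 = 19.7
- q = 15%: 30 × 0.5220 = 15.7
- q = 20%: 30 × 0.4096 = 12.3

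**2. Standard error (SE) of a difference between two conditions.** For complete-case ANOVA without visit it is √[2σ²(1−ρ)/n]. With σ = 1 and ρ = 0.5 this is √(1/n): 0.183 at n = 30, 0.225 at n = 19.7 and 0.285 at n = 12.3. The comparator is a mixed model on all available sessions with treatment and visit. Its SE was found by simulating random orders and missing patterns and averaging over the six pairwise contrasts.

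| Excess SE of complete-case analysis | 5% | 10% | 15% | 20% |
|---|---|---|---|---|
| ANOVA without visit, independent missing | 5% | 13% | 22% | 35% |
| ANOVA without visit, dropout after first scan | 0% | 3% | 5% | 9% |
| ANOVA with visit, independent missing | 8% | 17% | 28% | 42% |
| ANOVA with visit, dropout after first scan | 2% | 5% | 8% | 12% |
| Whole participants missing, visit in both models | 0% | 0% | 0% | 0% |

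Repeat runs agree to about one or two points. Rows 1 and 2 are the comparison for gaze, social learning and plasma. Rows 3 and 4 apply to analyses that already carry visit, and only if they delete listwise. With 50 patients, row 1 at 5/10/20% becomes about 6/15/36%, from variance ratios 0.884/0.761/0.540 and 1/√ratio.

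**3. Planned dose-versus-placebo t-tests.** Using available pairs, the paired t-test SE relative to the mixed model is 1.002/1.020/1.039/1.064 (independent) and 0.990/1.000/1.010/1.023 (dropout after first scan).

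**4. All-session GLM.** A GLM with participant as a factor that keeps every session has an SE only about 0.3 to 2% above the mixed model.

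**5. Visit term.** Suppose a linear drift of T within-person SDs from first to fourth visit. The four visit means have variance T²(¼ + 1/36 + 1/36 + ¼)/3 = 0.185T². Leaving visit out multiplies the SE by √(1 + 0.185T²): 1.02, 1.09 and 1.32 for T = 0.5, 1 and 2. Estimating visit costs about 1.9% in SE with 30 complete patients. Dividing by 1.019 leaves a net gain of about 0%, 7% and 29%.

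**6. Several values per session.** Gaze yields two values per session (emotional, neutral), the ball game two and connectivity three. In simulations at nominal 5%, with session variance 0.25 to 1 times residual, a participant intercept alone gave type I error of 9 to 18% with two values and 14 to 33% with three. One value per session gave 4.8 to 5.5%. With 10/20% of sessions missing independently and Kenward-Roger degrees of freedom, it was 5.7/5.2%.

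**The case against.** **The plan never states listwise deletion.** This stands. A reader might infer that incomplete patients will be excluded, but the documents do not say so. The imaging analyses are described as GLMs, two-stage for aim 1, and could keep every session, which would leave almost nothing to gain there.

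**The loss may be small or nil.** This also stands. The team aims for a similar number of tests at each visit, which makes scattered missing sessions less likely than dropout or a task a patient never does. Plasma is drawn five minutes after the spray and resting state is the first functional run, so fatigue should mostly spare both. The planned t-tests lose little.

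**The covariate check may cover visit.** It is too general to supply a visit term for gaze or social learning.

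**Two stronger readings fail.** A reader might infer that omitting visit biases the dose contrasts; with randomized order it does not. A reader might also add the analysis labelled aim 4 in Statistical analysis (responses to punishment and helpful behaviour). It matches no aim under Objectives, where Aim 4 is plasma oxytocin, and no scanner task described for the clinical visits. It is left out until those sections are reconciled.

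**A mixed model is partly preference.** With complete data and no drift it gains nothing. What remains is that incomplete data are expected and no rule exists.

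**Conclusion.** The concern holds as a minor point to consider. The missing rule, and the missing visit term for gaze and social learning, are certain from the text; the size of the loss is not. For outcomes whose ANOVA has no visit term, the complete-case SE would be 0 to 9% larger under dropout after the first scan and 5 to 35% larger under independent missingness, across 5 to 20% of sessions missing. The larger figures of up to 42% apply only to analyses that already carry visit and delete listwise, which the plan does not state. The net gain from a visit term is negligible at a drift of 0.5 within-person SDs and about 7% at 1 SD. The documents suggest no visit effect on plasma, so the visit point concerns gaze and social learning.

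These sizes rest on assumed rates, patterns, correlation and drift. The issue is precision and an unfixed analysis choice, not bias in the planned contrasts.

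**What to change.** Use the amendment route the plan already foresees, dated before the final analysis. Healthy subjects screening reports that testing of patients with autism is complete, and Randomization and blinding says "We will break the blind after testing 25 patients with ASD to check the results half-way for a mid-point analysis". The amendment should therefore name the outcomes already unblinded.

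- **Model.** For gaze, social learning, extracted region or network values and plasma, use a linear mixed model on all available sessions. Include treatment and visit number (1 to 4) as fixed factors, a participant random effect, Kenward-Roger degrees of freedom, and named dose-versus-dose and dose-versus-placebo contrasts.
- **One value per session.** By default enter one summary value or contrast per session, for example emotional minus neutral. A participant intercept alone is not adequate for several values per session.
- **Fixed in advance.** Do not let the choice of model depend on the observed missingness. Tabulate missing sessions by treatment, visit and reason as description only.
- **Keep.** Leave the whole-brain GLMs as planned, and report complete-case ANOVA as a sensitivity analysis.

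The cost is amendment text and modest analysis work. There are two downsides. The model assumes data are missing at random, which fatigue-driven omission may violate. It also costs about 2% in SE if data are complete and there is no drift.

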There will be analysis at various stages of the trial. We might need to analyze the behavioral and physiological data for data monitoring committee, in any or to write reports to NIH about the progress. There will be analysis of primary outcome measures of the different aims (cited above) during mid-way analysis (when we break the blind half way at  $N=25$  of ASD). The analysis will also be conducted at the final stage of the trial.

Brain imaging procedures using MRI, fMRI will be conducted at the Biomedical Imaging Technology Center (BITC) at Emory. Anatomical Image Acquisition: participants will be positioned supine in the MRI scanner (Siemens, Magnetom Prisma, Trio 3T) with instructions to lie motionless. Padded head restraint will minimize head movement during scanning sessions, each of which will begin with a 15 second scout scan to localize the position of the brain within the magnet. This will be followed by T1-weighted MPRAGE scan (TR= 2300 ms, TE = 4 ms, matrix = 256x256, FOV=256, slice thickness = 1.00 mm, gap = 0 mm).

**For aim 1, the primary outcome measure** consists of investigating the effects of different treatments (3 doses of oxytocin and one dose of placebo) on brain functional connectivity at rest in patients with ASD, using fMRI. During resting state functional image acquisition (8 minutes), participants will be asked to remain awake and not moving. Image acquisition will be obtained using a multi-band slice accelerated gradient echo-planar imaging (EPI) pulse sequence 179, 180 with the following parameters: TR = 1000 ms, TE = 24 ms, matrix = 74 x 74, FOV = 220 mm, slice thickness = 2.0 mm, 64 axial slices, to reduce magnetic susceptibility artifact in the OFC region.

The aim of this analysis is to determine whether there is target engagement for intranasal oxytocin by demonstrating differences between doses of IN-OT on BOLD rsFC or whether there is a simple oxytocin effect. We define target engagement OXT effect (TEE-OXT) as any differential effect between a dose of OXT from another dose of OXT on brain or behavior. We define oxytocin effect

(OXT-Effect) as any differential effect between oxytocin (any dose) and placebo administration in ASD.

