Initial preprocessing steps for single-subject resting-state fMRI data will be conducted with FSL software or SPM with the help and training of [name]. fMRI data will undergo standard preprocessing steps: realignment, slice-timing correction, volume registration, spatial normalization to MNI152 template, spatial smoothing with 5 mm FWHM Gaussian filter and temporal band-pass filtering (0.01-0.1 HZ). Corrections for head motion, whole-brain signals, ventricular signals, white matter signals. We will define specific regions of interest that includes the social brain network that we discussed in the sections above (MPFC, OFC, PCC, precuneus, insula, ACC, ventral striatum, amygdala, temporal areas, SMA etc). We will compare the functional connectivity between and within the different social brain networks (including the default, the salience network and temporal network) between the different treatment conditions. This analysis will be performed based on the GLM using corresponding regressors. We will also compute the rsFC between the different regions of interest by calculating a Pearson's correlation coefficient between the time series of the preprocessed functional MRI signals. In order to study target engagement effect on within network correlations, the resulting of the cross-correlation maps will be Fisher transformed to z-scores and fed into a 2-factor (4 treatment condition X 3 networks (default, salience, temporal); covariate: visit order) ANOVA. In order to study target engagement effect on between network correlations, the resulting of the cross-correlation maps will be Fisher transformed to z-scores and fed into a repeated Anova (4 treatment condition X 3 networks (Salience+Default; Salience+Temporal; Default+Temporal); covariate: visit order) ANOVA. In order to determine simple oxytocin effect, T-contrast maps will determine the differences in rsFC between placebo and each of the different doses of oxytocin. Multiple comparison correction will be conducted. The specificity of the results will also be conformed in a whole brain analysis. Given that baseline rs-FC is not acquired, and in order to account for non-specific fluctuations, we will use a two-stage GLM procedure during which we account for within-subject variability (across the different visits). Time regressor will be added to the model as a covariate to control for external factors that could influence rs-FC other than the treatment.

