**For aim 3:** *The primary outcome measure* of the third outcome measure consist of studying the different effects of treatments on BOLD activity of key brain regions (OFC, ventral striatum, inferior occipital cortex, fusiform gyrus, amygdala, superior parietal lobe, insula and ACC) while playing a social interactive ball-game in ASD. During this ball-game, we will analyze the BOLD brain activity during social output videos that will display either neutral or positive face expressions. We expect more rewarding brain regions to be more activated during the process of positive social feedback with oxytocin treatment. In order to determine TEE-OXT, we will conduct repeated ANOVA analysis with variables (BOLD activity in response to positive and neutral) and treatments (8, 24, 48, placebo). We will also investigate the general effect of TEE-OXT on the BOLD activity of socio-emotional brain regions in response to both positive and neutral faces with the variable (BOLD activity in response to all faces) and treatments. We will also investigate the differences between oxytocin treatment and placebo. We expect at least the doses of 24IU and 48IU to be different from placebo. Covariates such as visit order will be entered in the GLM model as a regressor to control for habituation effects.

*The secondary outcome measure* consists of studying the effects of treatments on behavioral outcome measure (post scanner on social learning). In this behavioral task, we will analyze the accuracy and reaction time in recognizing faces as familiar. We will conduct ANOVA and t-tests to compare the performance in these 2 variables (accuracy and reaction time) between the 4 treatment conditions.

**For aim 4:** *The primary outcome measure* of the fourth outcome measure consists of investigating the differences between treatments on the modulation of brain activity of reward brain regions in response to punishment and helpful behavior. In the GLM model, we will conduct an ANOVA or t-tests with 4 treatment conditions and the BOLD signal in NAcc, OFC, VTA and ACC.

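### Target engagement is defined as a difference between oxytocin doses but tested with ANOVAs that include placebo, so a flat oxytocin effect could be reported as target engagement

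*Combined protocol and SAP*

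**What the plan says.** All references are to the Statistical analysis section of the combined protocol and SAP, unless another section is named.

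- **Definition.** Under aim 1, TEE-OXT is defined "as any differential effect between a dose of OXT from another dose of OXT on brain or behavior". A separate term, OXT-Effect, covers any dose against placebo. The stated purpose is to tell the two apart.
- **Aim 1 primary.** "In order to study target engagement effect on within network correlations", the Fisher-transformed correlations are "fed into a 2-factor (4 treatment condition X 3 networks (default, salience, temporal); covariate: visit order) ANOVA". A second four-condition ANOVA handles between-network correlations. The only contrasts named are placebo against each dose.
- **Aim 2 primary.** "The presence of TEE-OXT will consist of finding differences between different treatment conditions of OXT and not only between OXT and placebo". No test is attached to this rule.
- **Aim 2 secondary (gaze duration, four treatment conditions).** "We will analyze the data with ANOVA repeated measures for determining TEE-OXT and t-tests for simple OXT-effects".
- **Aim 3 primary.** To "determine TEE-OXT, we will conduct repeated ANOVA analysis with variables (BOLD activity in response to positive and neutral) and treatments (8, 24, 48, placebo"). A second analysis looks at the "general effect of TEE-OXT on the BOLD activity of socio-emotional brain regions in response to both positive and neutral faces with the variable" being the response to all faces, by treatment.
- **Publication.** The plan may publish dose comparisons (labelled target engagement) separately from comparisons of 24 and 48 IU with placebo.

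**The concern.** The treatment factor in these ANOVAs has four levels and three degrees of freedom. One degree of freedom is placebo against the average of the three doses; the other two are differences among the doses. Only those two correspond to TEE-OXT as defined. The named test therefore answers whether any of the four conditions differ, which is a different question.

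The all-faces analysis in aim 3 is the clearest case. It has no valence factor, so it is a plain treatment main effect, yet it carries the TEE-OXT label.

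If the three doses are equivalent and all differ from placebo, the correct conclusion is an OXT-Effect without target engagement. A significant four-level test would not show this by itself, and the result could be published under the wrong one of the two headings.

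**Working it through.** **Inputs from the plan.** N=50 planned, N=30 thought achievable, and N=25 at the mid-point look (Randomization and blinding). d=0.32 with 95% CI 0.18-0.47 is the pooled effect cited when discussing behavioral measures (power paragraph). The same paragraph expects larger effects on brain measures.

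**Assumed, not in the documents.** Alpha 0.05, sphericity, and between-visit correlation rho of 0.3, 0.5 or 0.7; d is in single-visit SD units.

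**The plan's own power figure.** The plan gives N=50 for 95% power at d=0.2 with four treatments. In a one-group four-level repeated-measures F test this is met only for particular unstated correlations: about 0.55 if 0.2 is read as Cohen's f, or about 0.89 if d=0.2 is converted to f=0.1. At rho 0.5 the power is 93% and 35% respectively. The figure is not an input to what follows.

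**Step 1: four-level main effect when the doses are equal.** With means (0, d, d, d) the squared deviations from the grand mean (0.75d) sum to 0.75d². Hence lambda = N × 0.75 × d² / (1 − rho), noncentral F with 3 and 3(N−1) df. For N=50, d=0.32, rho=0.5: lambda = 50 × 0.75 × 0.1024 / 0.5 = 7.68, and the rejection probability is 0.621.

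| N | d | rho 0.3 | rho 0.5 | rho 0.7 |
|---|---|---|---|---|
| 50 | 0.18 | 0.168 | 0.222 | 0.354 |
| 50 | 0.32 | 0.468 | 0.621 | 0.855 |
| 50 | 0.47 | 0.824 | 0.936 | 0.996 |
| 30 | 0.32 | 0.287 | 0.392 | 0.613 |
| 25 | 0.32 | 0.241 | 0.328 | 0.523 |

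Simulation with 20,000 replicates (N=50, d=0.32) gives 0.470, 0.619 and 0.855.

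**Step 2: three-dose test, same scenario.** Its noncentrality is zero, so it rejects at alpha. Simulated: 0.051, 0.052 and 0.048.

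**Step 3: omnibus test followed by dose-pair t-tests.** Aims 1 to 3 do not state this procedure for TEE-OXT. Simulated false TEE-OXT at N=50, d=0.32, for rho 0.3/0.5/0.7: 0.102/0.111/0.119 with uncorrected pairs and 0.041/0.045/0.043 with Bonferroni.

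**Step 4: valence-by-treatment interaction in aim 3.** If the flat shift is equal for positive and neutral faces, the interaction stays near 5% (0.047-0.054, 8,000 replicates). The plan expects otherwise: "We expect more rewarding brain regions to be more activated during the process of positive social feedback with oxytocin treatment". If the shift occurs for positive feedback only, lambda = N × 0.75 × d² / (2 × ve), where ve is the within-visit residual share of variance (assumed). For N=50, d=0.32:

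- ve=0.5: lambda = 3.84 / 1.0 = 3.84, rejection 0.337
- ve=0.3: lambda = 3.84 / 0.6 = 6.40, rejection 0.535
- ve=0.2: lambda = 3.84 / 0.4 = 9.60, rejection 0.729

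So the interaction has the same weakness when the oxytocin effect depends on valence but not on dose.

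**Step 5: power of the three-dose test.** 2 and 2(N−1) df, N=50, rho 0.3/0.5/0.7.

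| True pattern | Squared deviations | d=0.32 | d=0.2 |
|---|---|---|---|
| Extremes differ by d, middle dose midway | d²/2 | 0.373/0.501/0.733 | 0.168/0.220/0.344 |
| One dose stands apart by d | 2d²/3 | 0.480/0.629/0.854 | 0.211/0.282/0.444 |

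**The case against.** The best reply is that the plan's intent is clear. The definition is general, applying to brain and behavior, so calling a flat oxytocin effect TEE-OXT would breach the plan's own terms. The Objectives section expects differences between doses for aim 1, and more gaze at higher doses than at smaller doses or placebo for the aim 2 secondary. The publication paragraph describes target engagement results as dose comparisons. On that reading the ANOVA is only a gatekeeper, dose comparisons follow as a matter of course, and the relevant error rate is 10-12% or 4-5% rather than 47-86%. Aim 1 also promises correction for multiple comparisons, and the end of the section defers analytic detail to amendments. Finally, the flat-dose scenario and several inputs are assumed, d=0.32 is offered for behavioral measures while two of the three analyses are imaging, and the all-faces sentence in aim 3 does not list its treatment levels.

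Much of this stands as evidence of intent, and no text makes the omnibus F alone the rule for declaring TEE-OXT. But intent does not supply a test. In aim 1 the only named contrasts are against placebo, and in the aim 2 secondary the t-tests are tied to the OXT-Effect. The correction sentence does not say which family it covers and appears only under aim 1. The gap between 10-12% and 4-5% shows that even on the favorable reading the follow-up must be specified. The deferred detail is to come once analysis work begins, while the blind is to be broken at N=25 to analyze primary outcomes. The aim 2 primary rule shows that the authors saw the risk; that caution is not carried into the other analyses.

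**Conclusion.** The concern holds. For aim 1, the aim 2 secondary and the aim 3 primary, the test assigned to TEE-OXT does not match its definition and can reject when the three doses are identical. That conclusion follows from the structure of the test and needs no numerical assumption.

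The size does depend on assumptions. With a flat effect of d=0.32, alpha 0.05, sphericity and correlation 0.3 to 0.7, the four-level main effect rejects in 47-86% of trials at N=50, 29-61% at N=30 and 24-52% at N=25. At the confidence limits of d with N=50 the ranges are 17-35% and 82% to over 99%. These are upper readings, which apply if the omnibus result is taken as target engagement. With dose pairs added, the rate is 10-12% uncorrected or 4-5% with Bonferroni. All figures are for a single measure. Larger imaging effects, which the plan expects, would raise the omnibus rates. The point should be corrected before results are examined by treatment.

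**What to change.** In aim 1, both aim 2 outcomes and the aim 3 primary:

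- State that TEE-OXT is tested by a 2-df contrast among 8, 24 and 48 IU within the same repeated-measures model and, where relevant, by the interaction of that contrast with network or valence.
- Follow it with dose-pair contrasts adjusted for multiplicity, and name the adjustment.
- Reserve contrasts with placebo for the OXT-Effect.
- Extend the aim 2 primary rule to every analysis that uses the TEE-OXT label, including the all-faces analysis in aim 3.
- Treat a linear dose trend as supplementary only, since it can miss a non-monotone difference.

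The plasma oxytocin analysis can stay as it is, because TEE-OXT is not assigned there.

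The cost is SAP wording and two contrast vectors per model, with no added data or visits. Fewer TEE-OXT findings should be expected. The claim of 95% power at d=0.2 with N=50 must be restated for the three-dose test, whose power under the assumptions above is 37-85% for a dose difference of 0.32 and 17-44% for 0.2, depending on the dose pattern and the correlation.
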